#### 7.8 Software

The single integrated analysis can only be carried out in a Bayesian framework. It remains to be decided whether existing Bayesian Markov Chain Monte Carlo packages (WinBUGS, OpenBUGS, JAGS, STAN) will be suitable for this, or other Bayesian computational packages, such as INLA. Given the size of the dataset and the use of non-standard likelihoods, it may be necessary to write a specific Gibbs Sampler and code the problem in C++ to be run on a multiple-processor machine.

## 8. Population epidemiology of ZIKV, DENV, CHIKV

We set out the SAP for population epidemiology as a series of specifications for tables, providing comments on the definitions of variables and their interpretation.

#### 8.1 Analyses to be carried out

Note that the estimates of incidence and seroprevalence that can be generated directly from ZIKA-VT are not true population estimates, because, within each collaborating center, the intention is to recruit pregnant women from areas at higher risk of arbovirus infection, and during periods of higher incidence. However, there is an interest in estimating incidence because it may correlate with risk of transmission or adverse clinical outcomes, if for example, both are related to viral load or degree of susceptibility.

All analyses will be initially stratified by center and mosquito season, or by center and year if there is no mosquito season. The text under each heading below should be understood as specifying one or more tables, in most cases separately for each of the three arboviruses.

8.1.1 Basic demographics of the sampled population. We will tabulate the numbers recruited each season, their age distribution. Further breakdowns will be by: socio-economic class, income range, type of housing, area of residence, residence stratified by arbovirus infection incidence (from surveillance data), as considered appropriate

8.1.2 Seroprevalence and cumulative incidence. For each arbovirus, the denominator for a seroprevalence estimate is the number of women who had at least one IgG test, and the numerator is the number who were IgG+ on their first test. In addition to "crude" (without adjustment) estimates of seroprevalence, we will obtain estimates of cumulative incidence  $\pi$ , which is (observed) seroprevalence p adjusted for IgG sensitivity and specificity, using the relationship

$$p = \pi Se + (1 - \pi)(1 - Sp)$$

Author: [name] (UNIVBRIS)

26

The sensitivity and specificity will be characterized as probability distributions based on the data available, assembled under the ZIKA-VID work package. The sources of this data will be continually updated (see *Appendix 4*).

If more than one test was used, results will be reported separately for each test (see Table 5)

The adjustment can be extended to account for cross-reactivity between DENV and ZIKV IgG tests, given information on sensitivity, general false positive rates, and cross-reactivity of both assays:

$$p_{Z} = \pi_{Z} S e_{Z} + (1 - \pi_{Z})(1 - S p_{Z}) + \pi_{D} X r_{Z}$$

$$p_{D} = \pi_{D} S e_{D} + (1 - \pi_{D})(1 - S p_{D}) + \pi_{Z} X r_{D}$$

This gives us two equations in two unknowns, and allows us to estimate the true cumulative incidence of both infections  $\pi_Z$ ,  $\pi_D$  from the observed seroprevalences  $p_Z$ ,  $p_D$ .

To bring together cumulative incidence estimates from multiple tests, the above methods for correcting for sensitivity and specificity can be extended to apply to *any number of tests*, and *any number of combinations of tests* (see Appendix 6).

**8.1.3** Proportion of symptomatic infections. For each infection, the denominator is the number of infected women, and numerator is the number of those reporting symptoms (according to pre-specified criteria) who were confirmed by PCR+, IgM+, or rising IgG. Infections which may either be ZIKV or DENV will be tabulated separately. We will investigate whether the proportion of symptomatic infections for each arbovirus is related to seroprevalence of the others.

8.1.4 Seroconversions and incidence of primary infections. The denominator is the number of women who were initially IgG- and who were retested on IgG at a later date. The numerator is the number of these women who were tested IgG+ at some later date. The time at risk is the total time between the first IgG- and either the first IgG+ if there was one, or the time between the first and last IgG- tests. Incidence of primary infection is found by dividing the number of seroconversions by total time at risk.

Once again, both crude and sensitivity-specificity-adjusted estimates will be considered, and separate estimates will be derived if there is more than one IgG test, using a similar format to *Table 5*.

Associations between incidence on one arbovirus and previous infections with the same or other arboviruses will be explored

8.1.5 IgM prevalence. The denominator is the number of women who were ever tested by IgM, and the numerator is the number whose first IgM test was a +ve. Separate analyses will be performed for different IgM tests, or tests on different samples.

Sensitivity and specificity will be taken into account, as above, and so will ZIKV-DENV cross-reactivity, to give adjusted estimates of IgM prevalence for each assay. Associations between IgM prevalence on one arbovirus and previous infections with the same or other arboviruses will be explored.

Author: [name] (UNIVBRIS)

27

8.1.6 Incidence of primary infections estimated by increase in seroprevalence. If we know or can estimate the cumulative incidence at a starting point T, then cumulative incidence at time t is related to incidence between t and T as follows:

$$\pi(t) = \pi(T) + (1 - \pi(T) \left( 1 - \exp\left( -\sum_{T \le u \le t} \lambda(u) \right) \right)$$

This can be modelled, for example assuming piece-wise constant incidence.

For DENV infection, which has been present for much longer, it may be preferable to model age-and time-specific cumulative incidence:

$$\pi(a,t) = \pi(a,T) + (1-\pi(a,T)\left(1-\exp\left(-\sum_{T \le u \le t} \lambda(a-T+u,u)\right)\right)$$

Using data from pregnant women, we would model incidence from time T and age 16 upwards.

These calculations assume that cumulative incidence can be estimated by adjusting seroprevalence for sensitivity and specificity as shown in *Section 8.1.2* 

8.1.7 Alignment with surveillance data: population estimates of incidence. Once estimates of incidence are available, they can be aligned with surveillance reports to estimate the proportion of incident infections (symptomatic or not) that are reported to the surveillance system. "Alignment" should be interpreted as putting the dates of the tests on the real timescale, so that incidence estimates for ZIKV, DENV, and CHIKV based on ZIKA-VT data can be compared to numbers of cases notified to national or regional surveillance centers, both confirmed and suspected.

If the estimated incidence in some period t is  $\lambda(t)$  and M(t) cases are reported in, say, the population of adult women aged 16-44, over the same time period and from the same area where ZIKA-VT is recruiting, then we can calculate the proportion of all infections that were reported over that time period as :

$$\theta(t) = \frac{M(t)}{N(1 - e^{-\lambda(t)})}$$

Where N is the relevant population size. This quantity can be examined over time to see if it remains relatively stable, and can be used in analyses of test persistence and adjustments for sensitivity and specificity needed to estimate the gestational age of maternal infection and vertical transmission rate (see Sections 5,7).

Further, once an estimate  $\theta(t)$  is available, it can be used to "gross-up" counts M(t), to estimate the true number of infections on a national or regional basis:  $M(t)/\theta(t)$ .

Sources of surveillance data for each collaborating center are listed in *Appendix 7*. These will be continually updated as new centers are included. The appendix will provide a description of the

Author: [name] (UNIVBRIS)

28

protocol under which surveillance for ZIKV, DENV, ZIKV is carried out, including: reporting definitions; criteria for "suspected" ZIKV, DENV, CHIKV; circumstances under which samples are collected and tested; and what tests are used.

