# APPENDIX 2. Role of Sensitivity, Specificity, Cross-reactivity in estimating gestational age at infection

We denote sensitivity, specificity, and cross-reactivity as Se, Sp, Xr. Cross-reactivity of, say, ZIKA IgM, is a special kind of false positive rate, in which a positive result on ZIKA IgM is obtained in a person who has not had a recent ZIKV infection but has had a recent DENV infection. For clarity, we distinguish this from other failures of specificity, although they too may be the result of cross-reactions.

The incidence *per week* of ZIKV infection in week t of pregnancy is  $\lambda(t)$ , so that the probability of an infection during t is  $1-e^{-\lambda t}$  and the probability of an infection during a period  $(t_1,t_2)$  is

$$1-e^{-\sum_{t_1\leq u\leq t_2}\lambda(u)}$$

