# Appendix 6. Estimating cumulative incidence by adjusting seroprevalence for test accuracy, with multiple tests

We anticipate that seroprevalence estimates will be based on more than one IgG test, and also that the number of tests each woman is tested on may vary. Here we describe how it will be possible to combine data from women tested in the same center/year tested only on IgG assay 1, with data from women tested only on IgG assay 2, and data from women tested on both assays, in a single coherent analysis. The methods can be extended to any number of tests.

If  $p_1,p_2$  are observed seroprevalence on the two IgG assays, we apply sensitivity and specificity corrections to each, around a common cumulative incidence parameter  $\pi$ , with  $p_1,p_2$  informed by independent Binomial data as discussed previously

$$p_1 = \pi S e_1 + (1 - \pi)(1 - S p_1)$$
  
$$p_2 = \pi S e_2 + (1 - \pi)(1 - S p_2)$$

In women who have been tested on both assays, the data is in the form of a cross-classification, which is multinomially distributed:  $r_{++}, r_{--}, r_{--}, r_{--} \sim Multinomial(p_{++}, p_{+-}, p_{-+}, p_{--}, n)$ , where

$$p_{ii} = \pi Se_{ii} + (1 - \pi)(1 - Sp_{ii}), \quad ij \in (++, +-, -+, --)$$

 $Se_{ij}$ ,  $(1-Sp_{ij})$  are the probabilities of obtaining results ij on the two tests in individuals who have had the infection, and in individuals who have not. This information on sensitivity and specificity will be obtained from studies in the ZIK-VID work package. Where this information is not available, weakly informative prior distributions for sensitivity and specificity of each test conditional on results from other tests, will be constructed based on results obtained where such data is available, and under guidance from the Expert Diagnostics Group.

This analysis can be further extended to account for cross-reactivity between ZIKV and DENV:

$$\begin{split} p_{Zij} &= \pi_Z S e_{Zij} + (1 - \pi_Z) (1 - S p_{Zij}) + \pi_D X r_{Zij} \\ p_{Dij} &= \pi_D S e_{Dij} + (1 - \pi_D) (1 - S p_{Dij}) + \pi_Z X r_{Dij} \end{split}$$

where  $Xr_{Zij}$  is the probability of obtaining a result ij on ZIKV antibody tests IgG-1 and IgG-2 in an individual who has been exposed to DENV (but not ZIKV). This data will be available from ZIKA-VID, or if not, suitably vague priors will be constructed.

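### The ZIKV–DENV cross-reactivity term in SAP 8.1.2 and Appendix 6 is added to terms that already cover every woman, so the Appendix 6 multinomial cells sum to 1 + pi_D and co-exposed women are counted twice

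*SAP*

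**What the plan says.** Section 8.1.2 first adjusts seroprevalence for sensitivity and specificity: p = pi·Se + (1 − pi)(1 − Sp). It then states that "The adjustment can be extended to account for cross-reactivity between DENV and ZIKV IgG tests" and gives, in plain notation:

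- p_Z = pi_Z·Se_Z + (1 − pi_Z)(1 − Sp_Z) + pi_D·Xr_Z
- p_D = pi_D·Se_D + (1 − pi_D)(1 − Sp_D) + pi_Z·Xr_D

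The pair is to be solved for the two cumulative incidences: "This gives us two equations in two unknowns".

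Appendix 6 repeats the same additive form for each result combination ij (++, +−, −+, −−) in women tested on two IgG assays, where the cross-classified data are described as data "which is multinomially distributed". Se_ij and (1 − Sp_ij) are defined there as probabilities of result ij in women who have, and have not, had the infection. Xr_Zij is likewise a result probability for the pair of ZIKV assays, and the population it refers to is given as "in an individual who has been exposed to DENV (but not ZIKV"). Appendix 2 defines IgM cross-reactivity in the same way, as a positive result "in a person who has not had a recent ZIKV infection but has had a recent DENV infection".

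Table 5 defines the reported cumulative incidence as adjusted for cross-reactivity, with the combined estimate taken from Appendix 6. Section 8.1.5 applies the same adjustment to IgM prevalence, and 8.1.6 builds on the 8.1.2 estimates.

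**The concern.** The first two terms of each equation split the population into infected (pi_Z) and uninfected (1 − pi_Z), and nobody is left over. The third term then adds a probability for every DENV-exposed woman. By the SAP's own definition Xr_Z does not apply to those who have also had ZIKV, and they are already counted in pi_Z·Se_Z. Women with DENV only are also counted twice, because the (1 − pi_Z)(1 − Sp_Z) term still covers them in full.

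At stake are the adjusted cumulative incidences for objective 2.2(i). A likelihood whose cell probabilities do not sum to 1 cannot be used as written, and solving the two-equation version attributes too many positives to cross-reaction.

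**Working it through.** **Inputs.** The equations and definitions come from 8.1.2 and Appendices 2 and 6. The SAP states no values for Se, Sp, Xr or prevalence, so all numbers below are assumptions. Write J = Se + Sp − 1.

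**1. Appendix 6 cells (no numerical assumption).** Se_ij, (1 − Sp_ij) and Xr_ij are each a set of probabilities over four exhaustive results, so each set sums to 1. Hence

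sum of p_Zij = pi_Z·1 + (1 − pi_Z)·1 + pi_D·1 = 1 + pi_D.

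The DENV cells sum to 1 + pi_Z. Without the cross-reactivity term the sum is 1, so the extension introduces the error.

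Example: assay sensitivities 0.95 and 0.90, false-positive rates 0.05 and 0.10, Xr 0.30 and 0.20, assays independent within class, pi_Z = 0.3, pi_D = 0.6. The cells (++, +−, −+, −−) are 0.296, 0.204, 0.164 and 0.936, total 1.60. At pi_Z = 0.1, pi_D = 0.5 the −− cell alone is 1.05.

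**2. Forward check of 8.1.2.** Se 0.95, Sp 0.97, Xr 0.30 for both assays, pi_Z/pi_D = 0.50/0.90:

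p_D = 0.90×0.95 + 0.10×0.03 + 0.50×0.30 = 0.855 + 0.003 + 0.150 = 1.008.

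At 0.30/0.80 the same equations give p_Z = 0.546 and p_D = 0.856, so values above 1 occur only toward the high end.

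**3. Bias on solving.** Generate seroprevalence from a model that partitions women, p_Z = pi_Z·Se + (1 − pi_Z)[pi_D·Xr + (1 − pi_D)(1 − Sp)], with independent exposures. At 0.50/0.90 and Xr 0.30:

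- p_Z = 0.475 + 0.50×(0.27 + 0.003) = 0.6115
- p_D = 0.855 + 0.10×(0.15 + 0.015) = 0.8715

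Solve the SAP pair with J = 0.92 and determinant 0.92² − 0.30² = 0.7564, after subtracting 1 − Sp = 0.03 from each p:

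- pi_Z = (0.5815×0.92 − 0.30×0.8415)/0.7564 = 0.37
- pi_D = (0.8415×0.92 − 0.30×0.5815)/0.7564 = 0.79

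The same steps give:

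| True pi_Z/pi_D | Xr | SAP solution |
|---|---|---|
| 0.50/0.90 | 0.10 | 0.44/0.86 |
| 0.50/0.90 | 0.30 | 0.37/0.79 |
| 0.50/0.90 | 0.50 | 0.32/0.75 |
| 0.30/0.80 | 0.10 | 0.26/0.78 |
| 0.30/0.80 | 0.30 | 0.22/0.75 |
| 0.70/0.90 | 0.30 | 0.54/0.75 |
| 0.10/0.10 | 0.30 | 0.095/0.095 |
| 0.01/0.50 | 0.30 | −0.009/0.504 |

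**4. Dependence on the generating model.** Suppose instead that cross-reaction adds to the general false-positive rate in all women without the target infection. Only the double count of co-exposed women then remains. With equal assay properties the error in each estimate is −pi_Z·pi_D·Xr/(J + Xr). At 0.50/0.90 and Xr 0.30 this is −0.135/1.22 = −0.11, giving 0.39/0.79. At 0.01/0.50 it is −0.0015/1.22 = −0.001, so the negative value in the last table row comes from the overlapping false-positive term and not from the co-exposed women.

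**5. A partial repair fails.** Multiplying only the last term by (1 − pi_Z) leaves Appendix 6 cells summing to 1 + (1 − pi_Z)·pi_D, which is 1.42 at 0.3/0.6. With the full partition the cells in step 1 become 0.2831, 0.1419, 0.0989 and 0.4761, total 1.00.

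**The case against.** The strongest reply concerns scope. These equations serve the population-epidemiology objective, not the two outcomes that section 10.4 calls fundamental. Section 8.1 itself says its estimates are not true population estimates, crude figures are reported alongside, and Appendix 6 plans consistency checks that might expose a misfit. All of that limits the consequences; none of it makes the Appendix 6 cells sum to 1. The wording that the adjustment can be extended does not make it hypothetical either, since Table 5 defines its reported quantity as adjusted for cross-reactivity. A2.2 admits simplifications about ZIKV and DENV occurring together, but for its own IgM formula; 8.1.2 and Appendix 6 carry no such caveat.

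A reader might infer three stronger things that the documents do not support:

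- *Modelled seroprevalence always exceeds 1.* In 8.1.2 it does so only when both prevalences and Xr are high.
- *Adjusted incidence is always too low.* For the double count alone, both estimates are low whenever each Xr is below its assay's J. Under the full partition this is not guaranteed: over wide random parameter ranges with Xr below J, both estimates were low in about 70% of sets.
- *The vertical transmission rate is therefore wrong.* Its false-positive correction has separate formulas in Appendix 2. The link runs only through incidence in 8.1.7, which can also come from seroconversions (8.1.4).

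For IgM (8.1.5), if both infections were at the 10% or 1% levels that 7.6 uses as illustrations, the solved values at Xr 0.30 would be 0.095 and 0.0097, a minor error.

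**Conclusion.** The formulas are wrong as written. The Appendix 6 result, cells summing to 1 + pi_D or 1 + pi_Z, follows from the SAP's definitions alone and invalidates the stated multinomial for any non-zero prevalence of the other virus. In 8.1.2 the double count usually pulls adjusted cumulative incidence down. The shortfall matters where both viruses are common: at 0.50/0.90 it is 0.06 to 0.18 for ZIKV and 0.04 to 0.15 for DENV across Xr 0.10 to 0.50. It is minor when both prevalences are low. At very low ZIKV prevalence with common DENV, the ZIKV estimate can fall below 0 while the DENV estimate is slightly too high. These sizes rest on assumed Se 0.95, Sp 0.97, equal Xr for both assays and independent exposures; they illustrate the error and do not predict the study's results.

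**What to change.** In 8.1.2 replace the pair with

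- p_Z = pi_Z·Se_Z + (1 − pi_Z)[pi_D·Xr_Z + (1 − pi_D)(1 − Sp_Z)]
- p_D = pi_D·Se_D + (1 − pi_D)[pi_Z·Xr_D + (1 − pi_Z)(1 − Sp_D)]

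and use the same form for each cell ij in Appendix 6. State two things with it. Sp now means specificity in women with neither infection, which is how A2.2 already describes its specificity term, so the ZIKA-VID inputs must be matched to that meaning. Exposures to ZIKV and DENV are assumed independent.

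This is a text change and needs no new data. Relaxing independence costs more. Four joint exposure states (both, ZIKV only, DENV only, neither) have three free prevalences, which two marginal seroprevalences cannot identify. That version needs the joint ZIKV-by-DENV result table with result probabilities for each state, or an informative prior on the association, and is better offered as a sensitivity analysis.

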#### 5.4 Taking test sensitivity, specificity and cross-reactivity into account

PCR tests can be regarded as effectively 100% specific, but they have a short detection window, which varies between individuals. We refer to this as the test's persistence distribution. Serological tests vary in their specificity and sensitivity. Failures of specificity (false positives) can arise for several reasons. While some may be due to a random signal that has exceeded the test's threshold, other false positives may be due to cross-reaction to antibodies to related viruses. Currently available DENV and ZIKV IgM tests react to each other's IgM, and to other flavivirus IgM. We can therefore anticipate that ZIKV and DENV IgM test specificity might vary between collaborating centers, reflecting the geographical distribution of other viruses to which they are cross-reactive. In addition, although IgM antibody is usually assumed to persist for 12 weeks, in some individuals it may persist for many months. Therefore, if IgM is due to an infection acquired many months before the pregnancy, we might regard it as an *analytic* true positive, but a *diagnostic* false positive.

Information on the effective sensitivity and specificity of IgG and IgM assays in different centers is currently incomplete, but will be systematically developed under the ZIKA-VID program. Sources of data on properties of diagnostic tests, for use in ZIKA-VT data analyses, will be updated regularly (see *Appendices 3 & 4*).

Reliable estimates of the sensitivity and specificity of each individual test are not, by themselves, enough to determine the probability that a woman has experienced an infection in pregnancy given her test results. Each woman will be tested on multiple occasions, and on multiple tests. Interpretation of these sequences of tests is complex as we can anticipate there are strong correlations, conditional on true infection status, both between tests results at the same time, and between tests of the same type over time. Rules for determining whether a sequence of tests and clinical findings should be considered as a reflecting a "confirmed", "definite" or "possible" maternal infection will be drawn up by the Expert Diagnostics Group (*Appendix 1*).

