#### 7.5.3 Estimating the persistence distributions of multiple tests

The ZIKA-VT protocol provides for

Author: [name] (UNIVBRIS)

23

- (i) PCR, IgM, and IgG tests on women with symptoms,
- (ii) PCR on all IgM+, IgG seroconversions, and rises in IgG titer.
- (iii) Repeat PCR, IgM, and IgG tests at the prescribed intervals until a first PCR-, IgM-, IgG falling titer, respectively.
- (iv) Use of serum, saliva, and urine samples.
- (v) Avidity tests may be used to determine if an infection is primary or secondary; this also carries information on timing of infection

Thus, each woman's record is likely to consist of a series of results on at least three tests and possibly more if more than one assay of each type is used.

The analysis above for a single test is readily extended to two or more tests k=1,2...K. The data on each individual i now consists of K sets of implied -++- sequences denoted  $U_{Li_k}, U_{Ri_k}, W_{Li_k}, W_{Ri_k}$ , and the parameter set is expanded to accommodate K distributions  $F_k(d,\theta_k)$ . The likelihood for the persistence tests for woman i is then:

$$\Pr\left(\begin{array}{c} (U_{Li_{k}}, U_{Ri_{k}}, W_{Li_{k}}, W_{Ri_{k}}) \mid \pi_{i}(t), \theta_{k} \end{array}\right) = \sum_{t} \pi_{i}(t) \prod_{k} \left( F_{k}(W_{Ri_{k}} - t - 1, \theta_{k}) - F_{k}(W_{Li_{k}} - t - 1, \theta_{k}) \right) \quad Max_{k}(U_{Li_{k}}) \leq t \leq Min_{k}(U_{Ri_{k}})$$

Note that, in this framework, the date of symptoms and the dates of short persistence tests such as PCR, are highly informative about the persistence distributions of longer persistence tests such as IgM and rising IgG.

Extension to multiple tests, use of a variety of tests, and changes in which tests are used, raises questions about the numbers of parameters that may need to be estimated. Our initial strategy will be to assume that the persistence distributions of all tests of the same type (PCR, IgM, rising IgG) have the same underlying parametric or semi-parametric form, with persistence distributions that differ only by a single parameter, for example based on a proportional hazards assumption. This constant would be estimated from the data. Persistence distributions for different *samples* (serum, saliva, urine) on the same test will be treated the same way.

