## 7.6 Accounting for imperfect test sensitivity and specificity, and cross-reactivity

As noted earlier, we need to calculate for each woman recruited into ZIKA-VT, the probability that she was infected in pregnancy, and the distribution of GA when this infection occurred, if it occurred at all, based on tests with imperfect accuracy.

Author: [name] (UNIVBRIS)

24

For example, a sequence of four ZIKV IgM- results throughout pregnancy, assuming there were no IgG, PCR tests and no symptoms, would be scored as "No evidence of maternal infection in pregnancy" in basic analyses, but there is a possibility that they are all false -ves.

As long as the testing algorithm is relatively sensitive, say 95% or more, the bias in estimates of the vertical transmission due to false -ves is likely to be negligible. A small proportion (<5%) of maternal infections would be missed from the denominator, but their babies will not be followed up, and so would also be missed from the numerator. The exception to this would be if they are not only congenitally infected but their congenital infection is apparent. But it can be shown that, on current evidence, this would lead to only a very slight over-estimation of the VTR.

The difficulties posed by false *positive* IgM tests are, however, far more serious. If the specificity of an IgM test is 95%, then 5% of uninfected mothers will receive false +ve results, and will be considered infected in pregnancy. If 10% of women are infected in pregnancy, then, for every 15 women considered as infected in pregnancy, only (approximately) 10 would be truly infected, and the vertical infection rate will be underestimated by a factor of 1.5. If incidence is lower, and only 1% of women are infected in pregnancy, then only 1 in 5 women being followed are truly infected and the vertical transmission rate will be underestimated by a factor of 5.

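### The proportion symptomatic in SAP 8.1.3 has no test-accuracy adjustment, so it can be biased in either direction, and its planned ZIKV–DENV association can arise partly from the tests

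*SAP*

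**What the plan says.** Objective 2.2(ii) is the share of infections that are symptomatic and how previous infection affects it. Section 8.1.3 gives the estimator: "For each infection, the denominator is the number of infected women, and numerator is the number of those reporting symptoms", restricted to women "who were confirmed by PCR+, IgM+, or rising IgG". A lone IgM+ therefore suffices. One safeguard is stated: "Infections which may either be ZIKV or DENV will be tabulated separately". An association follows: "We will investigate whether the proportion of symptomatic infections for each arbovirus is related to seroprevalence of the others".

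The neighboring sections differ. Section 8.1.2 adjusts seroprevalence for IgG sensitivity and specificity and extends this to ZIKV–DENV cross-reactivity. Section 8.1.4 says that "both crude and sensitivity-specificity-adjusted estimates will be considered". Section 8.1.5 adjusts IgM prevalence for all three. Section 8.1.3 mentions none of them.

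On detection, 7.5.3 provides for "PCR, IgM, and IgG tests on women with symptoms". Women without symptoms get PCR only after an IgM or IgG signal. On accuracy, 7.6 illustrates false-positive IgM at 95% specificity and 10% infected: "for every 15 women considered as infected in pregnancy, only (approximately) 10 would be truly infected". Section 5.4 states that ZIKV and DENV IgM assays react to each other's antibody, and that "ZIKV and DENV IgM test specificity might vary between collaborating centers".

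**The concern.** The ratio depends on how infections are found as well as on how often they cause symptoms.

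- **Symptom-dependent detection.** A woman with symptoms is tested on all three markers because of them. An infection without symptoms must first show itself serologically. If it is found less often, the ratio is too high.
- **False positives.** Uninfected women with a false IgM+ join the denominator, and join the numerator only if they report symptoms. If they do so less often than true cases, the ratio is too low; if more often, too high.
- **The association.** If the false-positive rate for ZIKV rises with DENV exposure, the ZIKV proportion symptomatic will move with DENV seroprevalence even when earlier DENV has no effect. Section 8.2.1 also anticipates that IgM persistence may differ after earlier ZIKV or DENV, so the chance of detecting an infection may itself depend on the exposure under study.

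At stake is objective 2.2(ii): a test artefact could be read as an effect of previous infection on symptoms.

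**Working it through.** **Inputs.** From SAP 7.6: specificity Sp = 95%; share infected p = 10% or 1%. Assumed, because the SAP gives no values: true proportion symptomatic s = 20%; symptom rate among false positives b = 0–10%; Sp = 99% as a better algorithm; sensitivity 95% with symptoms (Se_s) and 50–80% without (Se_a); cross-reactivity Xr = 2–10%.

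**Step 1: the plan's own figure.** Dilution factor = [p·Se + (1−p)(1−Sp)] / (p·Se). With p = 0.10, Sp = 0.95, Se = 1: (0.10 + 0.045)/0.10 = 1.45. Taking 5% of all women as false positives gives 0.15/0.10 = 1.5, as stated. At p = 0.01 the same formula gives 0.0595/0.01 = 5.95, where 7.6 states 5; that is a separate slip in the illustration.

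**Step 2: the observed ratio.** With f the false-positive rate:

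observed = [p·s·Se_s + (1−p)·f·b] / [p·(s·Se_s + (1−s)·Se_a) + (1−p)·f]

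**Step 3: false positives alone** (Se = 1, s = 0.20).

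| Sp | p | denominator | b = 0 | b = 0.10 |
|---|---|---|---|---|
| 0.95 | 0.10 | 0.145 | 0.020/0.145 = 13.8% | 0.0245/0.145 = 16.9% |
| 0.95 | 0.01 | 0.0595 | 0.002/0.0595 = 3.4% | 0.00695/0.0595 = 11.7% |
| 0.99 | 0.10 | 0.109 | 0.020/0.109 = 18.3% | 0.0209/0.109 = 19.2% |
| 0.99 | 0.01 | 0.0199 | 0.002/0.0199 = 10.1% | 0.00299/0.0199 = 15.0% |

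**Step 4: symptom-dependent detection alone** (Sp = 1, Se_s = 0.95). Se_a = 0.80: 0.19/(0.19 + 0.64) = 22.9%. Se_a = 0.50: 0.19/(0.19 + 0.40) = 32.2%. The bias is upward.

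**Step 5: both together** (p = 0.10, b = 0.05, Se_s = 0.95, Se_a = 0.60).
- Sp = 0.95: (0.019 + 0.00225)/(0.067 + 0.045) = 19.0%.
- Sp = 0.99: (0.019 + 0.00045)/(0.067 + 0.009) = 25.6%.

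The direction changes with specificity alone.

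**Step 6: the association.** Hold s at 20% everywhere, with p = 0.10, b = 0.05, Se = 1, and f = 0.01 + (DENV-exposed share × Xr). For shares of 10%, 50% and 90%:
- Xr = 0.10: 0.0209/0.118 = 17.7%, 0.0227/0.154 = 14.7%, 0.0245/0.190 = 12.9%.
- Xr = 0.02: 18.5%, 17.7%, 17.0%.

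A negative trend appears with no true effect. Appendix 2 defines cross-reactivity for recent DENV infection; if only recent infection cross-reacts, the relevant share is smaller and the trend shrinks.

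**Step 7: can it be corrected?** Apply the 8.1.2 relationship within each symptom group (p = 0.10, s = 0.20, b = 0.05, Sp = 0.95, Se_s = 0.95, Se_a = 0.60).
- With symptoms: 0.065 of women, positive fraction 0.02125/0.065 = 0.327; (0.327 − 0.05)/0.90 × 0.065 = 0.020.
- Without: 0.935 of women, positive fraction 0.09075/0.935 = 0.0971; (0.0971 − 0.05)/0.55 × 0.935 = 0.080.
- Ratio: 0.020/(0.020 + 0.080) = 20%.

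The true value returns exactly because the accuracy inputs are taken as known. This shows that the correction is feasible, not that it is robust to wrong inputs.

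**The case against.** The case for leaving 8.1.3 alone has substance. Section 10.4 treats every outcome other than vertical transmission and severe outcomes as hypothesis-forming. Section 8 specifies tables, initially stratified by center and season. The SAP leaves rules for classifying infection to the Expert Group (5.4, Appendix 1), so that the ratio is unadjusted is inferred from silence. Section 7.6 expects confirmatory tests and wants accuracy judged for the whole algorithm. Section 8.1 aims recruitment at higher-incidence areas and periods, where dilution is milder. PCR follows every IgM+ whatever the symptoms, and women already IgG+ can still be found by a rising titer. Section 8.3 offers Bayesian methods wherever adjustment is needed.

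This limits size and consequence but does not close the gap. Section 8.3 does not say that 8.1.3 needs adjustment. Algorithm accuracy is hoped for, not quantified. Separate tabulation of ambiguous infections leaves single-virus false positives in place.

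Stronger readings are tempting but unsupported:
- **A roughly six-fold understatement at 1% infected.** This needs a lone IgM test's specificity and no symptoms at all among false positives. With symptoms in 10% of them, the factor is 20/11.7 = 1.7.
- **A computed share of missed asymptomatic infections from 12-week mean IgM persistence.** This needs a distribution shape and visit gaps that the SAP does not give, and it ignores IgG seroconversion and rising titer.
- **Women set aside as ZIKV or DENV are mostly asymptomatic.** No section says so.

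**Conclusion.** The point holds in a limited form. Section 8.1.3 omits the adjustment that 8.1.2, 8.1.4 and 8.1.5 name, for a quantity that is a stated objective and that the SAP's own account of testing shows to be vulnerable. Neither size nor net direction can be fixed from the SAP: the ranges above rest on the assumed true proportion, symptom rate among false positives, sensitivities and cross-reactivity. With specific testing and 10% infected, the false-positive part is small; symptom-dependent detection can remain.

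A reader might infer that centers with more DENV will necessarily show a different ZIKV proportion. The documents support only that they could: specificity is said to vary possibly, and the two biases oppose each other. The artefact through cross-reactivity is documented for ZIKV–DENV, not for pairs with CHIKV. This should be amended, but it does not touch the study's two fundamental outcomes.

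**What to change.** Amend 8.1.3 as follows.

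1. Keep the crude ratio as a table labelled descriptive and unadjusted.
2. Add an adjusted estimate. Apply the 8.1.2 relationship, with its cross-reactivity extension for ZIKV and DENV, separately to women with and without symptoms. Give each group its own sensitivity for its detection route, and use algorithm-level accuracy as 7.6 requires. Form the proportion from the two adjusted counts.
3. In the adjusted estimate, allocate infections that could be either ZIKV or DENV by probability; still tabulate them separately.
4. Run the association with other-virus infection on the adjusted proportion, by the woman's own baseline IgG status.
5. Use restriction to scheduled samples only as a sensitivity analysis. As the main analysis it would discard PCR-confirmed symptomatic cases, and detection could still depend on symptoms, since 7.5.2 lists them as a possible influence on persistence.

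The cost is SAP wording, some modelling within the Bayesian approach already planned in 8.3, and wider intervals. The estimate will depend on accuracy inputs that are planned but not settled: Appendix A2.3 leaves open how algorithm accuracy will be calculated and applied to test sequences. Results should therefore be shown over a range of those inputs.
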